9. STATISTICAL METHODOLOGY

9.1 General

Data listings will be provided for all data that is databased. Summary statistics and statistical analysis will only be presented for data where detailed in this SAP. For continuous data, summary statistics will include the arithmetic mean, arithmetic standard deviation (SD), median, min, max and N; for log-normal data (e.g. the PK parameters: Area under the concentration versus time curve [AUC] and the maximum observed drug concentration [C_{max}] the geometric mean and geometric coefficient of variation [CV%] will also be presented. For categorical data, frequency count and percentages will be presented. Data listings will be provided for all subjects up to the point of withdrawal, with any subjects excluded from the relevant population highlighted. Summary statistics and statistical analyses will generally only be performed for subjects included in the relevant analysis population. For the calculation of summary statistics and statistical analysis, unrounded data will be used.

Mean change from baseline is the mean of all individual subjects' change from baseline values. Each individual change from baseline will be calculated by subtracting the individual subject's baseline value from the value at the timepoint. The individual subject's change from baseline values will be used to calculate the mean change from baseline using a SAS procedure such as Proc Univariate.

Data analysis will be performed using SAS® Version 9.4 or greater.

9.2 Demographics and Subject Disposition

Subject disposition will be listed. The demographic variables age, sex, race, ethnicity, body weight, height and body mass index will be summarized and listed. All other demographics will be listed only.

9.3 Pharmacokinetic Assessment

9.3.1 Pharmacokinetic Analysis

The PK parameter estimates will be determined using non-compartmental procedures in validated software program (Phoenix WinNonlin Version 6.4.1 or later).

Plasma concentrations of LY3314814 and [$^{13}C_4$ $^{15}N_3$]-LY3314814 will be used to determine the following PK parameters, when possible:

Final, 05 Jan 2018 Page 7 of 14

Parameter	Units	Definition
AUC(0-t _{last})	ng.h/mL and ng equiv•h/mL	area under the concentration versus time curve from time zero to time t, where t is the last time point with a measurable concentration
AUC(0-∞)	ng.h/mL and ng equiv•h/mL	area under the concentration versus time curve from time zero to infinity
DN AUC(0-t _{last})	ng.h/mL/mg and ng equiv•h/mL/mg	dose normalised AUC(0-t _{last})
DN AUC(0-∞)	ng.h/mL/mg and ng equiv•h/mL/mg	dose normalised AUC(0-∞)
$AUC(t_{last}^{-\infty})$	%	percentage of AUC(0-∞) extrapolated
C _{max}	ng/mL and ng equiv/mL	maximum observed drug concentration
t _{max}	h	time of maximum observed drug concentration
t _{1/2}	h	half-life associated with the terminal rate constant (λz) in non-compartmental analysis
CL/F	L/h	apparent total body clearance of drug calculated after extra-vascular administration (LY3314814 only)
V _Z /F	L	apparent volume of distribution during the terminal phase after extra-vascular administration (LY3314814 only)
V _{SS} /F	L	apparent volume of distribution at steady state after extra- vascular administration (LY3314814 only)
CL	L/h	total body clearance of drug calculated after IV administration ([13C4 15N3]-LY3314814 only)
$V_{\mathbf{Z}}$	L	volume of distribution during the terminal phase after IV administration ([13C4 15N3]-LY3314814 only)
V _{ss}	L	volume of distribution at steady state after IV administration ([13C4 15N3]-LY3314814 only)

Dose normalised (DN) PK parameters DN AUC(0- t_{last}) and DN AUC(0- ∞) will be calculated by dividing the PK parameter value by dose in mg.

Additional PK parameters may be calculated, as appropriate. The software and version used for the final analyses will be specified in the clinical study report. Any exceptions or special handling of data will be clearly documented within the final study report.

Formatting of tables, figures and abbreviations will follow the Eli Lilly Global PK/PD/TS Tool: NON-COMPARTMENTAL PHARMACOKINETIC STYLE GUIDE. The version of the tool effective at the time of PK analysis will be followed.

General PK Parameter Rules

 Actual sampling times will be used in the final analyses of individual PK parameters, except for non-bolus pre-dose sampling times which will be set to zero.

Final, 05 Jan 2018 Page 8 of 14

- C_{max} and t_{max} will be reported from observed values. If C_{max} occurs at more than one time
 point, t_{max} will be assigned to the first occurrence of C_{max}.
- AUC parameters will be calculated using a combination of the linear and logarithmic trapezoidal methods (linear-log trapezoidal rule). The linear trapezoidal method will be applied up to t_{max} and then the logarithmic trapezoidal method will be used after t_{max}. The minimum requirement for the calculation of AUC will be the inclusion of at least three consecutive plasma concentrations above the lower limit of quantification (LLOQ), with at least one of these concentrations following C_{max}. AUC(0-∞) values where the percentage of the total area extrapolated is more than 20% will be flagged. Any AUC(0-∞) value excluded from summary statistics will be noted in the footnote of the summary table.
- Half-life (t_½) will be calculated, when appropriate, based on the apparent terminal log-linear portion of the concentration-time curve. The start of the terminal elimination phase for each subject will be defined by visual inspection and generally will be the first point at which there is no systematic deviation from the log-linear decline in plasma concentrations. Half-life will only be calculated when a reliable estimate for this parameter can be obtained comprising of at least 3 data points. If t_½ is estimated over a time window of less than 2 half-lives, the values will be flagged in the data listings. Any t_½ value excluded from summary statistics will be documented in the footnote of the summary table.
- A uniform weighting scheme will be used in the regression analysis of the terminal log-linear portion of the concentration-time curve.
- The parameters based on the observed last quantifiable drug concentration (C_{last}) will be reported.

Individual PK Parameter Rules

- Only quantifiable concentrations will be used to calculate PK parameters with the
 exception of special handling of certain concentrations reported below the lower limit of
 quantitation (BQL). Plasma concentrations reported as BQL will be set to a value of zero
 when all of the following conditions are met:
 - The compound is non-endogenous.
 - The samples are from the initial dose period for a subject or from a subsequent dose period following a suitable wash-out period.
 - The time points occur before the first quantifiable concentration.
- All other BQL concentrations that do not meet the above criteria will be set to missing.
- Also, where two or more consecutive concentrations are BQL towards the end of a
 profile, the profile will be deemed to have terminated and therefore any further

Final, 05 Jan 2018 Page 9 of 14

quantifiable concentrations will be set to missing for the calculation of the PK parameters unless it is considered to be a true characteristic of the profile of the drug.

Individual Concentration vs. Time Profiles

- Individual concentrations will be plotted utilizing actual sampling times.
- The terminal point selections will be indicated on a semi-logarithmic plot.

Average Concentration vs. Time Profiles

- The average concentration profiles will be graphed using scheduled (nominal) sampling times.
- The average concentration profiles will be graphed using arithmetic average concentrations.
- The pre-dose average concentration for single-dose data from non-endogenous compounds will be set to zero. Otherwise, only quantifiable concentrations will be used to calculate average concentrations.
- Concentrations at a sampling time exceeding the sampling time window specified in the protocol, or ± 10%, will be excluded from the average concentration profiles.
- Concentrations excluded from the mean calculation will be documented in the final study report.
- A concentration average will be plotted for a given sampling time only if 2/3 of the
 individual data at the time point have quantifiable measurements that are within the
 sampling time window specified in the protocol or ± 10%. An average concentration
 estimated with less than 2/3 but more than 3 data points may be displayed on the mean
 concentration plot if determined to be appropriate and will be documented within the
 final study report.

Treatment of Outliers during Pharmacokinetic Analysis

Application of this procedure to all PK analyses is not a requirement. Rather, this procedure provides justification for exclusion of data when scientifically appropriate. This procedure describes the methodology for identifying an individual value as an outlier for potential exclusion, but does not require that the value be excluded from analysis. The following methodology will not be used to exclude complete profiles from analysis.

Data within an Individual Profile

A value within an individual profile may be excluded from analysis if any of the following criteria are met:

 For PK profiles during single dosing of non-endogenous compounds, the concentration in a pre-dose sample is quantifiable.

Final, 05 Jan 2018 Page 10 of 14

 For any questionable datum that does not satisfy the above criteria, the profile will be evaluated and results reported with and without the suspected datum.

Data between Individual Profiles

- If n<6, then the dataset is too small to conduct a reliable range test. Data will be analyzed
 with and without the atypical value, and both sets of results will be reported.
- If n≥6, then an objective outlier test will be used to compare the atypical value to other values included in that calculation:
 - a. Transform all values in the calculation to the logarithmic domain.
 - b. Find the most extreme value from the arithmetic mean of the log transformed values and exclude that value from the dataset.
 - c. Calculate the lower and upper bounds of the range defined by the arithmetic mean ±3*SD of the remaining log-transformed values.
 - d. If the extreme value is within the range of arithmetic mean ±3*SD, then it is not an outlier and will be retained in the dataset.
 - e. If the extreme value is outside the range of arithmetic mean ±3*SD, then it is an outlier and will be excluded from analysis.

If the remaining dataset contains another atypical datum suspected to be an outlier and $n \ge 6$ following the exclusion, then repeat step 2 above. This evaluation may be repeated as many times as necessary, excluding only one suspected outlier in each iteration, until all data remaining in the dataset fall within the range of arithmetic mean $\pm 3*SD$ of the log-transformed values.

Reporting of Excluded Values

Individual values excluded as outliers will be documented in the final report. Approval of the final report will connote approval of the exclusion.

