7. SAMPLE SIZE JUSTIFICATION

Up to 8 subjects may be enrolled and dosed to ensure that at least 6 subjects complete and have evaluable PK data.

This sample size is considered adequate for Phase 1 studies evaluating absolute bioavailability and is not intended to meet any a priori statistical requirement.

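### The SAP's between-profile outlier test would flag a valid value in about 25–31% of clean data sets at n = 6–8, and the plan contradicts itself on whether a flagged value is then removed

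*SAP*

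**What the plan says.** SAP 9.3.1, under the treatment of outliers between individual profiles, splits on the number of values. Below six, the SAP says "If n<6, then the dataset is too small to conduct a reliable range test", and both sets of results, with and without the atypical value, are reported. From six upward, "an objective outlier test will be used to compare the atypical value to other values included in that calculation". The steps are: take logs, find the value furthest from the mean, set it aside, and compute the mean ±3 SD of the rest. Step e then says "If the extreme value is outside the range of arithmetic mean ±3*SD, then it is an outlier and will be excluded from analysis". The test may be repeated, one value at a time, while at least six values remain.

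The opening of the same procedure reads differently. Application is optional, and the method identifies values for possible exclusion "but does not require that the value be excluded from analysis". It adds: "The following methodology will not be used to exclude complete profiles from analysis". At n≥6 the SAP promises that excluded values will be documented, but not that results will be given both ways.

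SAP 7 sets the size: "Up to 8 subjects may be enrolled and dosed to ensure that at least 6 subjects complete and have evaluable PK data". So six, the planned minimum, is also the smallest n at which the test is trusted. SAP 9.3.2 fits the primary mixed model to log dose-normalised AUC(0-∞) for oral and IV, and reports the oral:IV ratio with a 90% confidence interval. Neither section says whether the outlier test applies to those values.

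**The concern.** A ±3 SD limit sounds strict. With a known mean and SD, a normal value falls outside it with probability 0.0027, so a set of six would be flagged about 6 × 0.0027 = 1.6% of the time and a set of eight about 8 × 0.0027 = 2.2%. The SAP's test is not that test. The suspect value is chosen because it is the most extreme, and the SD is then estimated from the five to seven values left after it has been taken out. Both features make a flag much more likely.

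The primary result is one ratio and its interval from 6 to 8 subjects, so a single removed value can matter. If a valid oral or IV AUC is dropped, that subject no longer contributes a within-subject oral–IV comparison, which is the advantage that protocol 5.4 claims for the tracer design. The study is open-label and the value that starts the test is simply called atypical, without definition. The decision to run the test, and to act on it, can therefore be made after the data are seen.

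**Working it through.** The documents give no false-flag rate, power or precision figure, so there is nothing of the plan's own to reproduce.

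**Inputs.** From the SAP: n = 6, 7 or 8 values per formulation (section 7); log scale, limit of 3 SD, suspect value left out of the mean and SD (9.3.1); 90% interval (9.3.2). Assumed: log values are normal with no true outliers. The flag rate does not depend on the size of the SD. The oral–IV correlation is not given, so I use 0 to 0.9.

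**Step 1: flag rate for one set of values.** The distance of a value from the mean of the other n−1, divided by their SD and by √(1 + 1/(n−1)), follows a t distribution on n−2 df. A limit of 3 SD is therefore a t cut-off of 3/√(1 + 1/(n−1)). Because any of the n values can be the extreme one, the rate per set is close to n × P(|t| > cut-off).

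| n | t cut-off | df | P per value | n × P | Simulated (1,000,000 sets) |
|---|---|---|---|---|---|
| 6 | 3/√1.2000 = 2.739 | 4 | 0.0520 | 31.2% | 31.2% |
| 7 | 3/√1.1667 = 2.777 | 5 | 0.0390 | 27.3% | 27.3% |
| 8 | 3/√1.1429 = 2.806 | 6 | 0.0309 | 24.7% | 24.8% |

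This is the first pass. With the permitted repetition, at least two valid values are flagged in about 8% of sets at n=7 and 7% at n=8. At n=6 a first exclusion leaves five values, so no repeat is possible.

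**Step 2: the limit needed for a 5% rate per set.** The multiplier is t(1 − 0.05/(2n), n−2) × √(1 + 1/(n−1)), which gives about 5.3 (n=6), 4.7 (n=7) and 4.4 (n=8).

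**Step 3: effect on the 90% interval if every flagged value is dropped.** The rule is run once on oral log AUC and once on IV log AUC, and subjects with both values left are analysed (400,000 simulated trials per cell). Entries are for n = 6 / 7 / 8. Width is the mean relative to the full-data interval.

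| Correlation | Trials with at least one flag | Coverage | Width |
|---|---|---|---|
| 0 | 53 / 47 / 43% | 83.5 / 84.3 / 85.1% | 0.94 / 0.95 / 0.95 |
| 0.5 | 52 / 47 / 43% | 86.7 / 87.2 / 87.6% | 1.01 / 1.00 / 0.99 |
| 0.8 | 49 / 44 / 40% | 88.5 / 88.9 / 89.0% | 1.05 / 1.03 / 1.02 |
| 0.9 | 46 / 41 / 37% | 89.2 / 89.4 / 89.4% | 1.05 / 1.03 / 1.02 |

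A REML random-subject model that keeps the unpaired values is closer to the SAP's model. It was run on 4,000 trials per cell, with complete pairs − 1 as df in place of Kenward–Roger and a Monte Carlo error of about 0.5 points. Coverage at n = 6 / 8 was 85.5 / 86.3% at correlation 0.5, 86.6 / 89.1% at 0.8 and 89.6 / 90.1% at 0.9. Relative width was 0.99 to 1.06.

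**Step 4: the same rule on individual oral:IV ratios, for contrast.** Single-pass coverage is 80.2, 82.0 and 83.2% at n = 6, 7 and 8, and mean width is 0.88, 0.90 and 0.92 of the full-data width. With repetition, coverage is about 80, 80 and 81%.

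**The case against.** The strongest reply is that the procedure is a permission and not an automatic filter. Its opening says that it need not be applied, that it supports exclusion where scientifically appropriate, and that a flagged value need not go. It starts from a value that someone already finds atypical. A reader might infer from step 1 that a quarter to a third of trials would lose a valid value. The documents do not support that: 25–31% is the rate at which the test flags clean sets when it is run, and the rate of actual removal depends on choices that the SAP leaves open. This part of the reply stands.

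A reader might also infer that the 90% interval would be too narrow. That too goes beyond the documents. The primary model uses oral and IV AUC as separate values. When the test acts on those, the interval is narrower on average only at low correlation; at 0.8–0.9 it is slightly wider. High correlation is plausible, since both doses are given to the same subject at the same time, but it is an assumption. The coverage of 80–83% arises only if individual ratios are tested, and the SAP's parameter table lists no such ratio.

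A third tempting reading is that dropping one AUC breaks the promise not to exclude complete profiles. It need not: the profile still supplies its other parameters, plots and listings, and the mixed model can use the subject's other formulation.

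Finally, the study is for estimation only, its sample size "is not intended to meet any a priori statistical requirement", and exclusions are documented, so a reader could rerun the model. This limits the severity. It does not answer the point that step e and the opening give opposite instructions, or that a test described as objective flags clean data this often.

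**Conclusion.** The concern holds as a should-fix point. The flag rate of 31%, 27% and 25% at n = 6, 7 and 8 is firm: it follows from the SAP's own steps and needs only normal log values. It is some 11 to 19 times what ±3 SD suggests (24.7/2.2 to 31.2/1.6). The contradiction between step e and the opening is plain on the page, as is the gap in reporting: a flagged value at n≥6 gets less protection than an atypical value at n<6, although the test is at its weakest at n=6.

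The effect on the primary interval is less certain. Under mechanical use on the two AUCs, coverage on complete pairs is about 84–85%, 87–88% and 89% at correlations of 0, 0.5 and 0.8–0.9. At a plausible high correlation the loss is therefore small. The main harm is that the plan lets the primary estimate depend on a choice made after seeing the data, supported by a test that gives little evidence of a true outlier.

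**What to change.** 1. State in SAP 9.3.2 that the primary absolute-bioavailability model uses all evaluable dose-normalised AUC(0-∞) values and that the outlier test removes none of them.
2. At n≥6, report any outlier-excluded result next to the primary one as a sensitivity analysis, as the SAP already does for n<6.
3. Reword step e so that a value outside the limits is identified for that sensitivity analysis, in agreement with the opening of the procedure.
4. Optionally, if a screen is kept, use a limit that depends on n (about ±5.3, ±4.7 and ±4.4 SD at n = 6, 7 and 8 for a 5% false-flag rate), applied once.

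The cost is a few lines of SAP text and one extra model run. The downside is that a truly aberrant value stays in the primary estimate; the sensitivity analysis would show its effect.

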9.3.2 Pharmacokinetic Statistical Methodology

To quantify the absolute bioavailability of LY3314814, a mixed-effect analysis of variance (ANOVA) model will be applied to the log-transformed DN AUC($0-\infty$) of LY3314814 obtained after oral dosing and that of the IV administered [$^{13}C_4^{15}N_3$]-LY3314814. The model will contain formulation (oral or IV) as a fixed effect and subject as a random effect. The absolute bioavailability will be expressed as the ratio of the least-squares geometric means of the formulations (oral:IV) along with its corresponding 90% confidence interval.

Final, 05 Jan 2018 Page 11 of 14

Example SAS code:

```
proc mixed data=DATA alpha=0.1;
   class treatment subject;
   model log_pk = treatment / ddfm=kr;
   random subject;
   lsmeans treatment / pdiff cl alpha=0.1;
   ods output lsmeans=lsmeans;
   ods output diffs=diffs;
run;
```

Additional analysis may be conducted if deemed appropriate.

9.4 Safety and Tolerability Assessments

9.4.1 Adverse events

Where changes in severity are recorded in the Case Report Form (CRF), each separate severity of the AE will be reported in the listings, only the most severe will be used in the summary tables. A pre-existing condition is defined as an AE that starts before the subject has provided written informed consent and is ongoing at consent. A non-treatment emergent AE is defined as an AE which starts after informed consent but prior to dosing. A treatment-emergent AE is defined as an AE which occurs postdose or which is present prior to dosing and becomes more severe postdose.

All AEs will be listed. Treatment-emergent AEs will be summarized by severity and relationship to the study drug. The frequency (the number of AEs, the number of subjects experiencing an AE and the percentage of subjects experiencing an AE) of treatment-emergent AEs will be summarized by Medical Dictionary for Regulatory Activities (MedDRA) version 20.1 system organ class and preferred term. The summary and frequency AE tables will be presented for all causalities and those considered related to the study drug. Any serious AEs will be tabulated. Onset time of AEs will derived relative to the oral administration.

9.4.2 Concomitant medication

Concomitant medication will be coded using the World Health Organization (WHO) drug dictionary (Version March 2017). Concomitant medication will be listed.

9.4.3 Clinical laboratory parameters

All clinical chemistry, hematology and urinalysis data will be listed. Additionally clinical chemistry, hematology and urinalysis data outside the reference ranges will be listed.

Values for any clinical chemistry, hematology and urinalysis values outside the reference ranges will be flagged on the individual subject data listings.

Final, 05 Jan 2018 Page 12 of 14

9.4.4 Vital signs

Vital signs data will be summarized by treatment together with changes from baseline, where baseline is defined as Day 1 predose.

Furthermore, values for individual subjects will be listed.

9.4.5 Electrocardiogram (ECG)

ECGs will be performed for safety monitoring purposes only and will not be presented.

9.4.6 Hepatic Monitoring

If a subject experiences elevated alanine aminotransferase (ALT) $\ge 3 \times$ upper limit of normal (ULN), alkaline phosphatase (ALP) $\ge 2 \times$ ULN, or elevated total bilirubin (TBL) $\ge 2 \times$ ULN, liver tests will be performed to confirm the abnormality.

The subjects' liver disease history and associated person liver disease history data will be listed. Any concomitant medication of acetaminophen/paracetamol will be listed. Results from any hepatic monitoring procedures, such as a magnetic resonance elastography (MRE) scan, and a biopsy assessment will be listed, if performed.

Hepatic risk factor assessment data will be listed. Liver related signs and symptoms data will be summarized by treatment and listed. Alcohol and recreational drug use data will also be listed.

All hepatic chemistry, hematology, coagulation, and serology data will be listed. Values outside the reference ranges will be flagged on the individual subject data listings.

